Screening will be conducted in either 1) NHS clinical research facilities or 2) NHS rheumatology, podiatry or physiotherapy outpatient settings within participating sites depending on local arrangements. Screening will be undertaken by the direct care team initially, prior to confirmation of eligibility by study research nurses or AHPs depending upon local arrangements for study personnel.

2.6 Inclusion criteria: Participants will be included if they fulfil all of the following criteria:

- They are 18 years of age or over.
- They have received a clinician diagnosis of RA (ACR 2010 criteria) and have disease durations of less than 2 years from diagnosis.
- They have disease-related foot impairments defined as at least one of: self-reported foot pain, and/or the presence of foot and/or ankle joint synovitis/tenosynovitis detected during clinical examination by the rheumatologist or rheumatology nurse specialist.
- They are willing to participate in the study and provide written informed consent.
- They have sufficient English language abilities to participate in a dialogue-based intervention and undertake completion of written questionnaires.
- 2.7 Exclusion criteria:
 - Participants will be excluded if they fulfil any of the following criteria:
 - They are not able to undertake or complete the intervention (e.g. due to severe co morbid disease) identified by their consultant rheumatologist prior to screening, or the research nurse at screening.
 - They are unable or unwilling to provide informed consent
 - They are currently taking part in other non-medical intervention studies where the goal of the intervention is to improve lower limb function and/or gait.

2.8 Duration of treatment: The intervention period will be 12 weeks from the first clinical consultation with the physiotherapist/podiatrist.

2.9 Statistical and qualitative analyses: Evaluation of measurement properties of primary outcome measure candidates:-

- Minimal clinical important difference (MCID) [1] for each outcome measure will be calculated using participant's perceptions of the overall treatment effect at 12 week follow-up using a 7-point global rating of change scale. The minimal important difference for each measure will be calculated as the mean change score in participants who according to the anchor improved, minus the mean change score in participants who did not improve or whose symptoms worsened.

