- Longitudinal validity of the primary outcome measure candidates relative to the global rating of change scale will be evaluated. Associations of change scores will be determined through regression analyses between candidate outcome measures and the anchor.
- Responsiveness of the primary outcome candidates to intervention from baseline to 12-week follow-up will be evaluated using four different effect size statistics: the paired t-test, Cohen's d, standardised response mean (SRM) and the Guyatt index (GI).

[figure not shown]
2.10 Remaining analyses will focus on process measures. Analysis will include the following aspects:-

- Acceptability of the intervention will be evaluated using a 3-item acceptability questionnaire and analysed using descriptive statistics and thematic analysis of qualitative data (from participants and clinicians).
- Treatment adherence will be evaluated using: the Exercise Adherence Rating Scale (EARS) and will be summarised using descriptive statistics; and thematic analysis of qualitative data (obtained from participants and clinicians).
- Safety of the intervention will be determined by analysis of all reported adverse events and thematic analysis of qualitative data from participants and clinicians.

2.11 Intervention fidelity data will be gathered from participants and study intervention clinicians and analysed as follows:-

- Deviations from intervention protocols will be recorded using intervention checklists and will be analysed using descriptive statistics.
- Thematic analysis of qualitative data obtained from clinicians.
- Audio samples of clinician-participant consultations will be evaluated objectively by independent assessors using an intervention fidelity checklist and the motivational interviewing treatment integrity scale.
- Behaviour beliefs will be evaluated before and after the intervention using the Theory of Planned Behaviour Questionnaire and will be analysed using descriptive and non-parametric statistics.

3. Study Flowchart:

4. Schedule of assessments

Study procedure	Description	Visit 1 Baseline	Visit 2 12 weeks	>12<16 weeks*
Review Inclusion/Exclusion Criteria and confirm eligibility	Initial screening will be conducted by a member of the direct care team. Review of inclusion/exclusion criteria to confirm eligibility will be conducted by a trained study research nurse/AHP and will be recorded on an Eligibility Screening Form	✓		

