Calculation of meaningful levels of change: A two-step iterative approach will be adopted for the selection of the most suitable primary outcome measure for the main trial. To determine the minimal clinical important difference (MCID) for each outcome measure, participant's perceptions of the overall treatment effect will be recorded at 12 week follow-up using a 7point global rating of change scale (defined as change in walking ability) as a patient-rated anchor [101,102]: "Overall how has your walking ability changed since the start of the study?", with a 7-point Likert scale response ("Very much worse", "Much worse", "A bit worse", "No change", "A bit better", "Much better", "Very much better"). In the absence of a gold reference standard for measurement of gait ability in early RA, the first iteration will be to evaluate the longitudinal validity of the primary outcome measure candidates relative to the global rating of change scale. Linear associations of change scores will be determined through correlation statistics between candidate outcome measures and the anchor. Candidate outcome measures will be excluded at the first iteration if they do not achieve the minimum threshold of association ($r \ge 0.65$) with the anchor [101,103]. The minimal important difference for each remaining measure, will be calculated as the mean change score in participants who according to the anchor, improved, minus the mean change score in participants who did not improve or whose symptoms worsened [101,103,105].

Calculation of responsiveness: Responsiveness of the primary outcome candidates to intervention from baseline to 12-week follow-up will be evaluated using four different effect size statistics: the paired t-test, Cohen's d, standardised response mean (SRM) and the Guyatt index (GI) [103-108]. To aid interpretation of the effect size statistics, the following benchmarks will be used: negligible (<0.15), small (\geq 0.15 and <0.40), medium (\geq 0.40 and <0.75), large (\geq 0.76 and <1.10), very large (\geq 1.10 and <1.45) and huge effect size s (>1.45) [104]. The larger the effect size, the more responsive the outcome measure.

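### The planned MCID is an improved-versus-not-improved difference, not a minimal one

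*Protocol*

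**What the plan says.** Section 15 (Calculation of meaningful levels of change) states the aim: "To determine the minimal clinical important difference (MCID) for each outcome measure". The anchor is a patient-rated question on change in walking ability with seven answers: three grades of worse, *No change*, and three grades of better (*A bit*, *Much*, *Very much*).

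Measures are first screened on their correlation with this anchor: "Candidate outcome measures will be excluded at the first iteration if they do not achieve the minimum threshold of association", set at r ≥ 0.65. For the measures that remain, the minimal important difference is "the mean change score in participants who according to the anchor, improved, minus the mean change score in participants who did not improve". Participants who got worse also belong to that comparator. Section 2.9 gives the same contrast, so this is not a slip in one place. Neither section says which anchor levels count as improved.

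Section 2.9 also plans a regression: "Associations of change scores will be determined through regression analyses between candidate outcome measures and the anchor". It fixes neither direction nor coding, and section 15 speaks of correlation statistics instead.

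**The concern.** A minimal important difference should describe the smallest change that patients notice. The anchor collects what is needed for that, but the formula merges it away. Large improvers raise the first mean and worsened participants lower the second. The result is the distance between the average improver and the average non-improver, and it shifts with how many did very well or got worse in this sample.

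Minimal important difference is named in objective 1, and section 12.1 names meaningful levels of change as the gap the study should fill. A mislabelled figure could therefore be reported for up to four instruments and passed on to the design of the main trial.

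**Working it through.** The protocol states no MCID value, so there is no figure of its own to reproduce. The check concerns the formula.

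**Inputs from the protocol.** Seven anchor levels and the r ≥ 0.65 screen (section 15); 42 participants with 20% attrition (section 18), so 42 × 0.8 = 33.6, about 34 evaluable. **Assumed, because not given:** the spread of answers over the anchor, the relation between change and anchor, and the power and target of any later RCT.

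**Step 1: direction.** Score each measure so that positive change is improvement, and let m1 to m7 be mean change by anchor level from worst to best. The improved mean is a weighted average of m5, m6 and m7. The comparator mean is a weighted average of m1 to m4. If the means rise with the anchor, the first is at least m5 and the second at most m4. The planned contrast is therefore at least m5 − m4, which is *A bit better* minus *No change*. With strictly rising means, the two are equal only if nobody answers outside those two levels. A correlation of 0.65 or more broadly implies rising means but does not guarantee every step.

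**Step 2: size with equal steps.** Code the levels −3 to +3 and let change be one unit per level, so the one-step difference is 1. For the first distribution below:

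- improved mean = (1×0.25 + 2×0.18 + 3×0.07)/0.50 = 1.64
- comparator mean = (0×0.25 − 1×0.15 − 2×0.07 − 3×0.03)/0.50 = −0.76
- planned contrast = 1.64 + 0.76 = 2.40 steps

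**Step 3: size without equal steps.** A latent bivariate-normal model (2,000,000 draws) was used, with the correlation between change and the 7-level anchor set to 0.65 and the SD of change set to 1. RCT sizing is 1:1, two-sided 5%: n per arm = 2(2.8016/d)² for 80% power, and power for the one-step difference d₁ is Φ(d₁√(n/2) − 1.96).

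| Assumed shares, worst to best (%) | Equal-step ratio | Planned (SD) | One step (SD) | Ratio | n/arm at 80%: planned; one step | Power for one step if sized on planned |
|---|---|---|---|---|---|---|
| 3/7/15/25/25/18/7 | 2.40 | 1.07 | 0.43 | 2.46 | 14; 84 | 21% |
| 1/3/8/20/35/23/10 | 2.16 | 1.11 | 0.52 | 2.12 | 13; 58 | 27% |
| 3/7/15/35/25/12/3 | 2.08 | 1.08 | 0.54 | 1.99 | 14; 54 | 30% |
| 1/3/10/30/40/13/3 | 1.77 | 1.09 | 0.65 | 1.68 | 14; 38 | 40% |
| 0/0/20/40/40/0/0 | 1.33 | 1.17 | 0.90 | 1.31 | 12; 20 | 60% |

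The ratios are the same at r = 0.80. Required numbers scale with the ratio squared: 1.31² = 1.7 to 2.46² = 6.1. At r = 0.65 the planned contrast stays near 1.1 SD of change across all five distributions, so it mainly reflects the correlation and the two-way split. Section 15's own benchmarks put the boundary between large and very large at 1.10.

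**Step 4: if improved were narrowed to *A bit better* only.** Worsened participants would still be in the comparator. With equal steps the contrast becomes 1 minus the comparator mean: 1.76, 1.53, 1.63, 1.43 and 1.33 for the five rows. The excess shrinks but remains.

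**Step 5: precision of the one-step difference.** In these distributions 20% to 40% of participants fall in each key level, which is 34×0.20 = 6.8 to 34×0.40 = 13.6 people. With 8.5 in each level and a within-level SD of about √(1 − 0.65²) = 0.76, the SE is 0.76×√(2/8.5) = 0.37 and the 95% half-width 0.72. Around 0.43 this runs from about −0.29 to 1.15.

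**The case against.** **The protocol does not size the RCT on this figure.** A reader might infer that the main trial would be undersized. The document does not support that. Objective 1 uses measurement properties to select an outcome. Section 15 lists simplicity, correlation with the anchor and responsiveness as the considerations for that choice, without the MCID. Section 31 leaves the main trial to a separate protocol. The power figures also treat a within-person step as the between-arm difference to be detected, which the protocol does not say. This objection stands, and the harm is conditional.

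**The size is assumed.** This also stands: no anchor distribution or SD is given. The direction does not depend on it. Section 8.1 describes a heterogeneous course, from quick remission to persistently active disease, so answers in the outer levels are plausible.

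**The statistical analysis plan may define improved.** It may, and pooling all three better levels is only the natural reading. The protocol itself puts worsened participants in the comparator, however, so step 4 would still apply.

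**The method is referenced and deliberate.** The cited sources cannot be checked here. The point rests on the mismatch between the label and the contrast as written.

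**The replacement is imprecise.** True: the interval in step 5 covers zero and also the planned contrast of 1.07. That is a reason to report the interval, not to call the pooled contrast minimal.

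**Conclusion.** The point holds as a fault of definition and label. The contrast in sections 2.9 and 15 measures improved against not improved. If mean change rises with the anchor, it cannot be smaller than the one-step difference, and it varies with the sample's mix of answers. Under the assumed distributions it is about 1.3 to 2.5 times too large to be called minimal. Only if it were later adopted as the RCT's target difference would a trial sized at 80% power have roughly 20% to 60% power for the one-step difference.

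It should be fixed but need not hold up the study. No stated decision rule uses the MCID, and all seven anchor levels are recorded, so the right summary can still be computed from the same data.

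**What to change.** In sections 2.9 and 15:

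1. Define the MCID as mean change in *A bit better* minus mean change in *No change*, with a 95% CI.
2. Report mean change with CIs for every anchor category.
3. Give the slope from a regression of change score on anchor category as a supporting estimate, stating that it equals the one-step difference only if the steps are equal. Section 2.9 would need to fix the direction and coding of its regression.
4. Keep improved minus not improved only as a descriptive contrast, state which levels count as improved, and do not call it minimal.

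The cost is wording and a few more outputs, with no new data. The price is a wide interval for the MCID, which should be stated when the figure is passed on to the main trial.
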